#### 2.3.3 To assess the effect that KAP has on symptoms of existential distress and depression in patients with non-operable GI cancers as measured by the Spiritual Well-Being (FACIT-Sp)

Exploratory Endpoint: Mean change in score on FACIT-Sp from baseline to Day 30 post completion of intervention.

**2.3.4** To develop an algorithm with Storyline Health technology to rapidly discover the most predictive and information rich components in the assessment of existential distress and its treatment response.

Exploratory Endpoint: Identification of a behavioral phenotype that better predicts a response to ketamine intervention.

**2.3.5** To evaluate the completion rate of questionnaires using the Storyline platform.

Exploratory Endpoint: The percentage of questionnaires completed.

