**Feature Selection:** Storyline AI measures over 20,000 speech, vocal and facial features from the responses for each question and many are correlated or not useful for detecting some phenotypes of interest. Therefore, in this second step, Short Story technology performs a feature selection analysis that uncovers the most useful features for each tested question in an assessment for predicting a particular phenotype or outcome. The major objective is to uncover the best questions and features when the available data has limited sample size and classes are imbalanced. Our approach will involve implementing the qualitative mutual information (QMI) feature selection algorithm previously detailed by others and proven for high dimensional data, including microarray data for tens of thousands of genes (Nagpal and Singh, 2019). The algorithm will provide a score that combines random forest (RF) feature importance scores with mutual information to obtain a QMI value for each feature. QMI is more powerful than random forest (RF) importance or mutual information alone for feature selection, as previously described (Nagpal and Singh, 2018). In brief, RF will be applied to the speech, vocal and facial feature sets separately for each question and the importance scores of each feature will be calculated, as well as mutual information. RF importance scores will be converted to Preference scores and multiplied by the mutual information to define QMI values for each feature. The features will then be ranked by QMI values and features with a  $QMI > 0$  will be retained. The results will return the most useful speech, facial and vocal features for each question. The usefulness of the features is determined from their ability to differentiate the two classes in a study, such as control versus sick patients.

This approach has many advantages, including broad utility with few parameters to tune, applications to diverse data types with few samples and acceptable computational speed. RF importance scores are powerful for ranking correlated features. Mutual information, which determines the amount of information one random variable can provide about another variable, is then incorporated to further help remove irrelevant and redundant features. When accounting for accuracy and computational efficiency, this combined approach outperforms most methods, including filter, wrapper, embedded and hybrid feature selection strategies (Nagpal and Singh, 2019).

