**Question Selection:** The final step of the Short Story algorithm will provide a score that determines the individual questions that should be retained in a new assessment and those that can be eliminated. In this approach, the input is all of the candidate questions and their optimized speech, vocal and facial features revealed from Short Story Score #2. The individual questions and question combinations that show the most value for predicting the classes of interest will then be determined. We will create a simple two-layer neural network that is architected to take Storyline speech, vocal and facial features as inputs to predict the

phenotypic classes of interest. The algorithm will be designed such that questions are tested in all possible pairwise combinations with 5-fold cross validation. The mean accuracy for predicting the target phenotype is determined for each question combination. Each pairwise question combination is then assigned an index. To compute the Short Story score for each question, we multiply the index and the mean classification accuracy for all question pairings in which that question was included in the predictive model. This vector of index\*accuracy values is summed to yield a score and then the scores for all of the candidate questions are min-max scaled to create the final Short Story question ranking score from 0-to-100, where a high score indicates important questions, and a low score indicates questions that can be pruned. The final results will return the ranking for each question and the mean classification accuracy values for each question.

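### Storyline results are scored and reported on raw classification accuracy alone, in about 12 patients and with no stated fold unit, so accuracy can look good when the questions carry no information

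*Combined protocol and SAP*

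**What the plan says.** Section 3.3.2 (Question Selection) feeds speech, vocal and facial features to a two-layer network, in which "questions are tested in all possible pairwise combinations with 5-fold cross validation". It continues: "The mean accuracy for predicting the target phenotype is determined for each question combination". The ranking is then built in two steps. First, "Each pairwise question combination is then assigned an index". Second, for each question, "we multiply the index and the mean classification accuracy for all question pairings in which that question was included" in the model; these products are summed and rescaled to 0-100. Low-scoring questions may be dropped, and the mean accuracies are returned as results.

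The Feature Selection paragraph of the same section gives the setting: "The major objective is to uncover the best questions and features when the available data has limited sample size and classes are imbalanced". It describes the classes only by a generic example, judging features by "their ability to differentiate the two classes in a study, such as control versus sick patients". The endpoint under objective 2.3.4 is: "Identification of a behavioral phenotype that better predicts a response to ketamine intervention".

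Section 5.5.1 sets enrolment at 12, and Section 9.2 replaces patients who never start therapy. The Schedule of Events places the Storyline assessment at the preparatory visit and at 14, 30 and 90 days. Section 9.5 calls the exploratory analysis descriptive and adds no rule on folds, stratification or a reference level for accuracy.

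**The concern.** Raw accuracy has no fixed no-information level. It depends on the class split, and when one class is larger a model that ignores its inputs scores well above 50%. An accuracy of 75% may therefore mean something or nothing, and the plan supplies no benchmark for telling which.

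The second gap is the fold unit. Face and voice identify a person. If several visits of one patient enter as separate rows and rows are assigned to folds at random, the network can recognise the patient and recall the label without learning anything about the phenotype.

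The output at stake is which questions survive into a new assessment and what accuracy is quoted for them. Section 3.1 says the study will inform a larger randomised trial, so an inflated accuracy or a wrongly dropped question could be carried forward.

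**Working it through.** The documents give no accuracy, class definition or class split for Storyline, so there is no figure to reproduce. The splits, sensitivities and correlations below are assumptions. The 12 patients and the up to four visits come from the plan.

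**1. Constant rule against an informative question.** With M of 12 patients in the larger class, always predicting that class scores M/12. A question with sensitivity = specificity = s classifies X ~ Binomial(12, s) patients correctly at any split, treating patients as independent. With s = 0.70:

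| Split | Constant rule M/12 | P(X < M) | P(X = M) | P(X > M) |
|---|---|---|---|---|
| 6/6 | 50% | 3.9% | 7.9% | 88.2% |
| 8/4 | 67% | 27.6% | 23.1% | 49.3% |
| 9/3 | 75% | 50.7% | 24.0% | 25.3% |
| 10/2 | 83% | 74.7% | 16.8% | 8.5% |

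With s = 0.80, P(X < M) is 0.4%, 7%, 21% and 44%.

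**2. The same comparison on balanced accuracy.** The constant rule now scores (100% + 0%)/2 = 50% at every split. At 9/3, let a ~ Bin(9, 0.7) and b ~ Bin(3, 0.7) be the correct calls in each class. The informative question falls below 50% when a/9 + b/3 < 1, that is, a + 3b < 9:

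- b = 0: 0.027 × P(a ≤ 8) = 0.027 × 0.960 = 0.026
- b = 1: 0.189 × P(a ≤ 5) = 0.189 × 0.270 = 0.051
- b = 2: 0.441 × P(a ≤ 2) = 0.441 × 0.004 = 0.002
- b = 3: impossible

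The total is about 8%, against 51% on raw accuracy. At 10/2 the figure falls from 75% to 11%.

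**3. Fold composition.** Five folds of 12 patients hold two or three patients each. Three minority patients can occupy at most three folds, so at least two folds contain none (2.4 on average under random allocation). With two minority patients the average is 3.1.

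**4. Record-level against patient-level folds.** Simulated data: 12 patients × 4 records, labels unrelated to the features, a 6/6 split, and features correlated within patient.

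| Classifier | Within-patient correlation | Folds by record | Folds by patient |
|---|---|---|---|
| Ridge, 50 features, 400 data sets | 0.3 to 0.7 | 74% to 96% | 41-42% |
| Nearest neighbour, 20 features, 1,000 data sets | 0.3 / 0.5 | 67% / 86% | about 45-46% |
| Nearest neighbour | 0 | 49% | 45% |

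At correlation 0 the record-level inflation disappears, so it comes from recognising the patient. At 9/3, ridge gives 82-96% by record and 66-68% by patient. Balanced accuracy does not cure this: for nearest neighbour at 9/3 and correlation 0.5, record-level balanced accuracy is still 86%, against 45% by patient.

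**5. The pair index.** The plan does not say how it is assigned. Suppose it is a running number and every pair has the same accuracy. Four questions give pairs 1-2, 1-3, 1-4, 2-3, 2-4, 3-4 with indices 1 to 6. The index sums are:

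- question 1: 1 + 2 + 3 = 6
- question 2: 1 + 4 + 5 = 10
- question 3: 2 + 4 + 6 = 12
- question 4: 3 + 5 + 6 = 14

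After min-max scaling the scores are 0, 50, 75 and 100, although no question is better than another.

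**The case against.** **The plan does not say that folds ignore the patient.** A reader might infer record-level splitting from the bare mention of 5-fold cross-validation, but the text names no unit. Predicting response from the baseline assessment is a natural reading of the endpoint. It gives one row per patient, and a split by record is then already a split by patient. This stands, and the figures in step 4 are conditional on pooled visits. Pooling is not far-fetched: Section 4 has the platform used throughout the study to build and refine biomarkers, and Sections 3.3.3 and 3.3.4 repeat the weekly story and the memory and attention tasks.

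**Imbalance is not a forecast for this trial.** The sentence on imbalanced classes is general platform text. Its example contrasts sick patients with controls, and this trial has no controls. This stands too: the plan describes such a setting but defines no classes.

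**The constant rule is a benchmark, not the fitted model.** Fitted to uninformative features at 9/3, with one row per patient, ridge averaged about 66%, below the 70% of the informative question. Step 1 also compares single questions, whereas the plan scores pairs. With fitted models, balanced accuracy improved the ranking only slightly. Its main gain was that uninformative features scoring 62-73% on raw accuracy at 9/3 read as about 45-49%. So step 2 overstates the likely gain in ranking, while the problem of reading the reported accuracy remains.

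**The objective is exploratory and descriptive.** That limits the consequences. It does not make an accuracy without a reference level interpretable.

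**Conclusion.** The point holds for the performance measure. Raw accuracy is the only one named, it serves both the score and the report, and it can reach 67-83% with no information at splits from 8/4 to 10/2. That range follows from arithmetic alone. The 51/24/25% comparison also assumes a 9/3 split and 70% sensitivity and specificity; at 6/6 the chance of scoring below the constant rule is only 4%.

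On folds, the supported statement is that the plan does not state the unit. If visits are pooled and split by record, uninformative features can reach roughly 70-96% at 6/6 for within-patient correlations of 0.3-0.7, against about 41-46% with patient-level folds. If one record per patient is used, this problem does not arise.

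A reader might also infer that questions are ranked on accuracy alone. They are ranked on a sum of index × accuracy, and the undefined index can set the order by itself, so changing the measure without settling the index would not make the ranking interpretable.

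The sample is about 12: replaced non-starters could add a few baseline records. Only objective 2.3.4 is affected; feasibility, safety and the prevalence of existential distress are not.

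**What to change.** In Sections 3.3.2 and 9.5:

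- Score questions on balanced accuracy computed once from the pooled out-of-fold predictions. It cannot be computed within folds that lack a class.
- Keep all records of a patient in the same fold, and stratify folds by class where numbers allow.
- Report each result beside the majority-class rate and a reference distribution from permuting labels at patient level. The permutation is needed because small-sample cross-validation is biased below 50% when there is no information. With leave-one-patient-out and 12 patients, balanced accuracy averaged 0.42 (6/6) and 0.45 (9/3), and pooled AUC 0.41 and 0.39. Switching to AUC alone would not remove this bias.
- Remove the pair index, or define it so that it cannot set the ranking by itself.
- Define the two classes and state which visits enter the model.

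The cost is a few lines of text and code, with no new data or visits. Reported performance will be lower, and with 12 patients it will remain imprecise.

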### **3.3.3 Psychiatric and Psychology Assessment Components:**

This part of the assessment is a 60-minute program broken into six 10-minute assessments of (i) physical symptoms, (ii) mood & emotion, (iii) cognition, (iv) homeostasis (ie. eating, sleeping, activity patterns) (v) social support and (vi) psychological associations. The program was created, in part, with our collaborator, [name] MD PhD (clinical psychiatrist) from a proven set of psychiatric interview questions and methods for DSM-5 diagnoses of depression, bipolar, anxiety, psychosis, neurocognitive disorders (dementia and delirium), suicidality, addiction, trauma and physical health. This interview uses open-ended questions that evaluate RDoC domains and create a caring and natural interview experience that is non-threatening using “normalization”, “reduction of guilt” and “symptom exaggeration” techniques, as well as providing safety, transparency, education and logical flow. Cognition is assessed, in part, using established clinical tests of cognitive functioning, including tests of (i) orientation (date, day of the week, location), (ii) short-term memory, (iii) long-term memory and recall, (iv) semantic fluency, (v) verbal fluency, (vi) working memory, (vii) attention and (viii) self-initiation. In addition, open-ended questions are included that ask for descriptions of (1) concerns about brain functioning, memory, concentration and fatigue, (2) any noticeable changes in memory or thinking, brain fog, headaches, (3) social interactions and perceived support, and (5) a 1-5-minute story about “something that happened to you this week”. The psychological associations assessment uses open-ended descriptions (“What does this make you think of?”) to capture responses to neutral, positive and negative cues, including Eckman faces (neutral, happy, sad, angry, disgust, surprise, contempt), Open Affective Standardized Image Sets (OASIS) and Affective Norms for English Words (ANEW) with valence, arousal or dominance characteristics predictive of mental illness (ie. death, cruelty, trouble, carefree, good, and praise). Finally, the Storyline assessment includes the standard PHQ-2, GAD-2 and PCL-2 questionnaires of clinical depression, anxiety and trauma symptoms as internal controls for clinical symptomology.

The neurological assessment developed by Storyline is 10 minutes long and is similar to a standard of care neurological exam. It includes questions that test eye movement, facial expression, speech, finger movements, hand movements, cognition and drawing. The material for this assessment is derived from the following leading clinical neurology textbook: “Neurological Examination Made Easy 6th Edition” by Geraint Fuller MD FRCP.

### **3.3.4 Deep Cognitive and Behavioral Assessments During Treatment**

Participants will be asked to perform a 10-minute “Well-being” assessment that includes open-ended questions about major domains of health. Examples include how they are, concerns, physical symptoms, emotional symptoms, social interactions and perceived support, medications and missed pills, energy and activity, sleep, a 1-5-minute story describing something that happened to them during the week and tests of short-term memory, working memory and attention.

## **4 STUDY DESIGN**

This study is an open-label feasibility study that will enroll a total of 12 patients with non-operable GI cancers suffering with existential distress. The study intervention for KAP will include a preparatory session, a total of three 2.5-3 hour therapy sessions which will occur 2-7 days apart, an integration session, and follow-up visits at 14, 30, and 90 days. Ketamine will be administered at a starting dose of 0.5 mg/kg and can be titrated up to 1.2 mg/kg based on patient response. The sessions will utilize eye-shades and a music track played over headphones. This will involve a therapist trained in KAP present 1:1 for all sessions with a physician available on site for medical evaluation, medication administration, support and backup.

We hypothesize that this study design will be feasible and ketamine can be administered safely. This study will better characterize the category of ‘existential distress’ which is variably described in the literature, separable as a phenomenon from DSM 5 mood and anxiety disorders, and a set of symptoms that cause significant distress for patients and care givers. To better characterize and understand symptoms and predictors of existential distress we will administer an existential distress screening instrument (the Existential Distress Scale) along with a broad psychosocial assessment to screen for patient enrollment as well as examine psychosocial predictors. We will then utilize the Storyline Health platform through the study process to build and refine a set of behavioral biomarkers to characterize existential distress.

### **4.1 Study Duration**

Study duration will be approximately 1 year.

### **4.2 End of Study**

A subject is considered to have completed the study if he or she has completed all phases of the study including the last visit or the last scheduled procedure shown in the Schedule of Events.

The study will end when the last subject completes the last visit or last contact, discontinues from the study, or is lost to follow-up, whichever occurs first. In addition, the sponsor may terminate the study at any time. If at any time, the sponsor terminates the study any subjects receiving clinical benefit from the study intervention may roll over to an expanded access protocol, if available, to ensure continued access to the study medication.

## 5 STUDY POPULATION

Potential study participants must meet all inclusion criteria and no exclusion criteria to be deemed eligible for trial participation. To ensure subject safety, all subjects must be deemed eligible at the time of study registration and must continue to meet eligibility criteria up to ketamine dosing. This eligibility checklist is used to determine subject eligibility and will be filed with the enrolling investigator's signature in the subject research chart.

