	
 
• Screen positivity for existential distress on the EDS, defined as scoring <math>\geq 3</math> on any of the 10 component domains, or a total score <math>\geq 6</math>
 
• ECOG Performance Status <math>\leq 2</math>.
 
 
Key Exclusion Criteria:
 
 
• Personal history or first- or second-degree relatives with schizophrenia, bipolar affective disorder, delusional disorder, schizoaffective disorder, psychosis, or other psychotic spectrum illness.
 
• Currently meeting DSM-5 criteria for Dissociative Disorder, or other psychiatric conditions judged to be incompatible with the establishment of rapport or safe exposure to ketamine.
 
• Currently meeting DSM-5 criteria for Cluster B Personality Disorder.
 
• Severe depression requiring immediate standard-of-care treatment (e.g., hospitalization).
 
• Suicidal ideation over the past month as assessed as a yes to question 3, 4, or 5 on the Columbia-Suicide Severity Rating Scale, Suicidal Ideation section
 
• Cancer with known CNS involvement, previously treated brain metastasis, or other major CNS disease.            Current or history within the last two years of meeting DSM-V criteria of substance use disorder (excluding caffeine and nicotine). Current substance use disorders may be identified through the drug urine screening test.
 
• Congestive heart failure, including all New York Heart Association Classes.
 
• Angina pectoris, cardiac hypertrophy, cardiac ischemia, myocardial infarction
 
• Uncontrolled hypertension at the time of enrollment (BP<math>>140</math> systolic or 90 diastolic), coronary artery disease, artificial heart valve
 
• Prolonged or congenital long QT syndrome (<math>>450</math> ms), serious cardiac arrhythmias, tachycardia, a clinically significant screening ECG abnormality
 
• History of hypersensitivity to ketamine
 
• Receiving ketamine treatments for psychiatric condition within the past 6 months
 
• Seizure disorder
 
• Moderate to severe dementia
 
• History of significant traumatic brain injury
 
• Requires the use of supplemental oxygen.
 

--	---

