## 5.2 Exclusion Criteria

1.  Received ketamine treatments for a psychiatric condition within 6 months of enrollment.
2.  Personal history or first- or second-degree relatives with schizophrenia, bipolar affective disorder, delusional disorder, schizoaffective disorder, psychosis, or other psychotic spectrum illness.
3.  Currently meeting DSM-5 criteria for Dissociative Disorder, or other psychiatric conditions judged to be incompatible with the establishment of rapport or safe exposure to ketamine.
4.  Currently meeting DSM-5 criteria for Cluster B Personality Disorder.
5.  Severe depression requiring immediate standard-of-care treatment (e.g., hospitalization).
6.  Suicidal ideation over the past month as assessed as a yes to question 3, 4, or 5 on the Columbia-Suicide Severity Rating Scale, Suicidal Ideation section
7.  Cancer with known CNS involvement, previously treated brain metastasis, or other major CNS disease.
8.  Current or history within the last two years of meeting DSM-V criteria of substance use disorder (excluding caffeine and nicotine). Current substance use disorders may be identified through the drug urine screening test.
9.  Current evidence of uncontrolled, significant intercurrent illness including, but not limited to, the following conditions:
  - Cardiovascular disorders:
    - Any grade congestive heart failure, unstable angina pectoris, serious cardiac arrhythmias including tachycardia, or clinically significant screening ECG abnormalities.
    - Cardiac hypertrophy or artificial heart valve.
    - Stroke (including transient ischemic attack [TIA]), myocardial infarction (MI), or other ischemic events, or thromboembolic event (eg, deep venous thrombosis, pulmonary embolism), and/or significant coronary artery disease within 3 months before the first dose.
    - QTc prolongation defined as a QTcF > 450 ms.
    - Known congenital long QT.
    - Uncontrolled hypertension defined as  $\geq 140/90$  as assessed from the mean of three consecutive blood pressure measurements taken over 10 minutes.

- Seizure disorder
- Moderate to severe dementia
- History of significant traumatic brain injury
- Requires the use of supplemental oxygen.
- Renal insufficiency as defined as creatinine clearance < 40 mL/min calculated by Cockcroft-Gault formula

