#### **6.2.2 Screening prior to ketamine-assisted psychotherapy:**

- Evaluation and screening **prior to first visit**
  - Psychiatric evaluation and review of medical history
  - Physical exam
- Evaluation and screening **immediately prior to each administration**
  - Confirm allergy list
  - Confirm patient has been NPO (except for water) for at least 4 hours prior to treatment
  - Medication history
    - Confirm no use of sedatives or psychostimulants for 12 hours prior to treatment
    - Confirm no use of MAO inhibitors for 2 weeks prior to treatment
  - Brief physical assessment
    - Blood pressure
      - If blood pressure > 140/90 mmHg, then make a clinical decision regarding risks/benefits of administration of ketamine
      - If blood pressure > 160/100 then hold ketamine and re-check after five minutes. May repeat this process twice.
      - If blood pressure remains over 160/100 then ketamine will not be given.
    - Other parameters that must be met for ketamine administration
      - Oxygen saturation > 92% on room air
      - Respirations > 8 breaths per minute
      - Patient must be fully awake
      - Patient must be able to move all extremities
  - Verify the patient has a responsible adult to escort them home
    - Patients may take any mode of transportation as long as they are accompanied by an escort
    - Ketamine will not be administered if an escort cannot be identified

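### A sustained pre-dose blood pressure above 140/90 and up to 160/100 is ineligible under Sections 5 and 5.2 but may be dosed under Section 6.2.2, clearly so at session 1

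*Combined protocol and SAP*

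**What the plan says.** Four places in the combined protocol and SAP set or apply a blood pressure limit.

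- **Section 5 (Study Population)** gives the general rule: "Potential study participants must meet all inclusion criteria and no exclusion criteria to be deemed eligible for trial participation". It then extends that rule in time. On grounds of subject safety, subjects must be eligible at registration and "must continue to meet eligibility criteria up to ketamine dosing".
- **Section 5.2, criterion 9** defines uncontrolled hypertension as 140/90 or higher, "as assessed from the mean of three consecutive blood pressure measurements taken over 10 minutes".
- **Section 6.2.2** lists checks to be made "immediately prior to each administration". One step reads: "If blood pressure > 140/90 mmHg, then make a clinical decision regarding risks/benefits of administration of ketamine". The next reads: "If blood pressure > 160/100 then hold ketamine and re-check after five minutes". The re-check may be repeated twice, and ketamine is refused only if pressure is still over 160/100. No averaging is specified.
- **Section 1.1 (Synopsis)** words the exclusion as "Uncontrolled hypertension at the time of enrollment", with a limit of more than 140 systolic or 90 diastolic and no averaging.

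No section says that Section 6.2.2 overrides the continuing-eligibility rule, or that blood pressure is exempt from that rule.

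**The concern.** The plan gives two answers to one practical question: may a patient whose pressure is raised but not above 160/100 on the dosing day receive ketamine? Sections 5 and 5.2 together say that the patient is no longer eligible. Section 6.2.2 says that a physician may decide.

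Two things are at stake. First, this is a cardiovascular safety limit, and the physician at the session needs one rule. Second, there is the trial record. Section 10.5 defines a deviation as any noncompliance with protocol requirements and asks for corrective action, documentation and reporting to the IRB under its policy. Section 8.4 has the DSMC review deviations, in a trial classed as high risk. A dose given within the terms of Section 6.2.2 could be logged as a deviation by one monitor and as compliant by another.

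**Working it through.** There is no stated figure to reproduce, so the check is a comparison of the rules.

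**Step 1. Set the rules side by side.**

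| Place | When it applies | Cut-off | Measurement | Consequence |
|---|---|---|---|---|
| Section 1.1 | Enrolment | >140 systolic or >90 diastolic | Not stated | Excluded |
| Section 5 with 5.2 (criterion 9) | Registration, then until dosing | ≥140/90 | Mean of three readings in 10 minutes | Not eligible |
| Section 6.2.2, first step | Before each administration | >140/90 | Not stated | Clinical decision |
| Section 6.2.2, second step | Before each administration | >160/100 | Re-check after 5 minutes, repeatable twice | Hold; refuse if still above |

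**Step 2. Pass a sustained pre-dose pressure through them** (sustained meaning that the three-reading mean is at the stated level).

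- Below 140/90: no rule bites, so there is no conflict.
- Exactly 140/90: criterion 9 excludes (≥), while Section 6.2.2 does not even call for a clinical decision (>). This is a difference at a single value and is mainly editorial.
- Above 140/90 and up to 160/100, for example 150/95: criterion 9 is met, so under Section 5 the subject is not eligible at dosing. Section 6.2.2 allows dosing on clinical decision. **The rules conflict.**
- Remaining over 160/100: criterion 9 is met and Section 6.2.2 refuses ketamine. The rules agree.

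**Step 3. Which sessions?** Section 6.2.2 covers every administration. The Section 5 phrase reaches at least the first dose, but does not say whether it means that dose or each of the three. Session 1 is therefore covered by both rules on any reading. Sessions 2 and 3 are covered by both only if the phrase means every dose. The planned decisions within reach are 12 first doses (12 × 1), or 36 administrations (12 × 3) on the wider reading. These are ceilings on how often the check is made, not estimates of how often pressure falls in the band.

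**Step 4. Can criterion 9 be applied on the day?** In the Schedule of Events, vital signs are planned at screening (window of 60 days) and at the ketamine sessions, with none at the preparatory session. Its footnote places the pre-session reading within ten minutes beforehand. The session check is thus the only planned measurement after screening that could show continued blood pressure eligibility. Neither that footnote nor Section 6.2.2 asks for the three-reading mean, so staff are given no stated way to apply criterion 9 at that moment.

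**The case against.** The best defence is that criterion 9 is an enrolment test and Section 6.2.2 is the dosing-day rule. Three places support it: the synopsis wording, the Schedule of Events (which marks eligibility criteria at screening only) and Section 5.3 (which requires eligibility before registration). Section 5 also mentions neither blood pressure nor Section 6.2.2, so the conflict appears only when Sections 5 and 5.2 are read together. This shows that an enrolment-only intention is plausible. It does not remove the Section 5 sentence, which expressly carries eligibility past registration and makes no exception.

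Other objections narrow the point, and they stand:

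- A reader might infer that any single reading above 140/90 both bars and permits dosing. It does not. Criterion 9 needs a mean of three, so one isolated high reading does not meet it.
- A reader might infer that Section 6.2.2 directs dosing in this band. It does not. It calls for a risk/benefit decision, which may be to withhold, and a physician who withholds complies with both rules. The conflict is between a bar and a discretion.
- A reader might count all 36 administrations as affected. The text clearly supports only the first dose.

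**Conclusion.** The inconsistency is real and limited. For a sustained pre-dose pressure above 140/90 and up to 160/100, the protocol makes the subject ineligible and also lets a physician dose. This is clear at session 1 and unresolved at sessions 2 and 3. It rests on reading Section 5 as written and on a three-reading mean in that band.

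Its size cannot be stated. The documents give no frequency of such pressures, and a share of single readings in the band would not measure the overlap, which needs a mean of three.

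A reader might also infer that the conflict could change the primary result. The documents do not establish that. Completion requires at least 2 of 3 sessions, so one withheld session leaves 3 − 1 = 2 and the subject still completes. Success requires at least 9 of 12 completers. For a subject barred before any dose, Section 9.2 provides replacement while Section 9.3 counts every enrolled subject as evaluable, so even that case has no settled effect on the completion rate. The supported consequences are an unclear safety limit on the day and an unclear deviation status afterwards.

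**What to change.** Reconcile Section 1.1, Section 5, Section 5.2 (criterion 9) and Section 6.2.2 so that all four state the same thing on three points:

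1. whether the eligibility blood pressure limit applies at enrolment only, up to the first dose, or before each dose;
2. the cut-off, including whether the boundary value itself is in or out;
3. how pressure is measured for that purpose.

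Then cross-reference Section 6.2.2 to the eligibility rule and say which governs on the dosing day, so that the deviation status under Section 10.5 follows directly. Which limit applies, and when, is for the clinical team; this review does not propose one. The cost is amendment wording, with no change to the sample size or the analyses.
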